## 6.8 Appendix 8: Data derivation rules

Not applicable.

## **6.9 Appendix 9: AEs of Special Interest**

The AEs of special interest for BRV (by preferred term) are as follows: autoimmune nephritis, nephritis, nephritis allergic, tubulointerstitial nephritis, and uveitis syndrome.

## **6.10 Appendix 10: Potentially Clinically Significant Criteria for safety endpoints**

Not applicable.

## **6.11 Appendix 11: Compliance**

Any dosing deviations will be assessed in the Data Evaluation Meeting (DEM) for possible impact on the PKS. No listing will be provided since study participant compliance to treatment will be ensured by the administration of IMP under the Investigator's (or designated site personnel's) supervision.

## **6.12 Appendix 12: Standard Reporting Procedures**

### **6.12.1 PK concentrations**

When reporting individual data in listings the following rules will apply:

- Missing data will be reported as NV (no value).
- Concentrations below the limit of quantification will be reported as BLQ (below the limit of quantification).
- Concentrations will be listed to the same number of significant figures supplied by the bioanalytical laboratory.

When reporting individual data in figures the following rules will apply:

- BLQ values prior to  $C_{max}$  will be set to 0 for purposes of plotting the figure (to capture lag-time) only for the linear plot.
- Actual sampling times will be used.

When summarizing the data in tables the following rules will apply:

- To calculate descriptive statistics, BLQ values will be set to half the LLOQ value and missing values will be excluded.
- When the total number of BLQ and missing values exceeds one third of the total then only minimum and maximum will be reported for this time point. Other descriptive statistics will be reported as missing ("‐"). The minimum will be reported as "BLQ".
- When the summary statistic includes one or more replaced BLQ values then a footnote will be included to say, "contains one or more BLQ value replaced by half the LLOQ value".

- A minimum of 3 values are required to calculate summary statistics. If only 2 values are available, then these will be presented as the minimum and maximum with other descriptive statistics reported as missing (“-”).
- If no participants have data, only n=0 will be presented. The other descriptive statistics will be left blank.
- Descriptive statistics for plasma concentration data will be reported to the same level of precision as the individual data for the minimum and maximum, and to 1 additional decimal place or 1 additional significant figure – depending on the reporting format of the original data with a maximum of 3 significant digits, i.e., 35.12 will be 35.1, 0.0004649 will be 0.000465 - for the mean (arithmetic and geometric), median, SD and the 95% CI for the geometric mean.
- Geometric CV will be reported as a percentage to 1 decimal place.

When summarizing the data in figures the following rules will apply:

- The data plotted in the figure will match the data presented in the summary table, with the exception of missing values prior to  $C_{max}$  which should be set to 0 in the figure (to capture lag-time).
- Nominal sampling times will be used.

Both linear and semi-logarithmic scales will be presented.

### **6.12.2 PK parameters**

When reporting individual data in listings the following rules will apply:

- Individual PK parameters will be reported to 3 significant figures.
- If a parameter cannot be calculated, it will be reported as NE (not estimable i.e., if input data is missing which prevents calculation) or NC (not calculable i.e., if the data were available but the calculation was considered unreliable).

When summarizing the data in tables the following rules will apply:

- The derived PK parameters will be considered as source data and this data without rounding will be used for calculation of summary statistics of PK parameters.
- Descriptive statistics will be reported to 4 significant figures for the mean (arithmetic and geometric), median and standard deviation (SD) and to 3 significant figures to the others including the 95% CI for the geometric mean.
- Geometric CV will be reported as a percentage to 1 decimal place.

• If at least two thirds of the participants have a PK parameter reported then descriptive statistics will be calculated, otherwise only minimum and maximum will be reported for this PK parameter and all other descriptive statistics will be reported as NE (i.e., not estimable).

- A minimum of 3 values are required to calculate summary statistics. If only 2 values are available, then these should be presented as the minimum and maximum with other descriptive statistics reported as missing (“-“)

## 6.13 Appendix 13: PK parameter calculations

Pharmacokinetic parameters will be calculated by non-compartmental analysis methods from the concentration-time data following these guidelines:

- Actual time will be used in the calculation of all derived pharmacokinetic parameters.
- There will be no imputation of missing data.
- BLQ values at the beginning of a subject profile (i.e., before the first incidence of a measurable concentration) will be assigned to zero. Embedded BLQ values (i.e., occurring between two measurable data points) and BLQ values occurring post- $C_{max}$  will be considered missing.

Pharmacokinetic parameters will be estimated according to the guidelines presented in [Table 6-1](#).

**Table 6-1: Pharmacokinetic Parameter and Estimation**

Parameter	Guideline for Derivation
$C_{max,ss}$ , $C_{trough}$ , $t_{last}$ and $t_{max,ss}$	Obtained directly from the observed concentration-time data
$AUC_{last}$	
The AUC from zero time (predose) to the time of last quantifiable concentration will be calculated by a combination of linear and logarithmic trapezoidal methods. Unless specifically requested and justified, the linear up/log down trapezoidal method will be employed.
 
The <math>AUC_{last}</math> is the sum of areas up to the time of the last quantifiable sample:
 $AUC_{last} = \int_0^t C_{last} * dt$
$AUC_{tau}$	
The AUC over the dosing interval will be determined for multiple dose studies using the linear up/log down trapezoidal rule.
 
In case <math>t_{obs}</math> is < <math>\tau</math> and <math>t_{obs}</math> is the last non-BLQ/non-missing sample, <math>AUC_{tau}</math> will be calculated by extrapolation to time <math>\tau</math> using lambda z. If the elimination phase cannot be characterized, <math>AUC_{tau}</math> will be set to missing.
 
<math>AUC_{tau}</math> values will be flagged based on the PK Scientist's judgement, based on the reliability of extrapolation.
 
Note: <math>t_{obs}</math> is the actual sampling time at planned timepoint <math>\tau</math>.

$\%AUC_{ex}$	The percentage of $AUC_{tau}$ obtained by extrapolation will be calculated as follows:

Parameter	Guideline for Derivation
	$\%AUC_{ex} = \frac{AUC_{tau} - AUC_{last}}{AUC_{tau}} \times 100$ 
<math>\%AUC_{ex}</math> should not exceed 10% for an individual profile. If the <math>\%AUC_{ex}</math> is more than 10%, the individual result should be flagged as all parameters depending on <math>AUC_{tau}</math> (i.e. <math>AUC_{tau}</math>, and <math>CL_{ss/F}</math>) should be flagged and footnoted in parameter listing. If <math>\%AUC_{ex}</math> is greater than 10% in more than 20% of the participants, the validity of the study may need to be discussed.

$\lambda_z$ and $t_{1/2}$	
 
1. The apparent terminal phase rate-constant (<math>\lambda_z</math>) will be estimated by linear regression of concentration versus time data presented in a log-linear scale.
 
2. Data are primarily monotonically decreasing in magnitude and are representative of the actual decline in the log concentration-time curve.
 
3. Only those data points that are judged to describe the terminal log-linear decline will be used in the regression.
 
4. A minimum number of three data points in the terminal phase will be used in calculating <math>\lambda_z</math> with the line of regression starting at any post-<math>C_{max}</math> data point (<math>C_{max}</math> should not be part of the regression slope). The adjusted correlation coefficient (<math>R^2</math> adjusted) in general should be greater than 0.90. Any value <math>< 0.90</math> but <math>\geq 0.8</math> will be flagged but may be used at the PK Scientist's best knowledge and judgment. All the derived parameters (i.e. <math>\lambda_z</math>, <math>t_{1/2}</math>, <math>AUC_{tau}</math>, <math>CL_{ss/F}</math>) will be flagged accordingly.
 
5. The interval used to determine <math>\lambda_z</math> should be equal or greater than 1.5-fold the estimated <math>t_{1/2}</math> or otherwise flagged and used for descriptive summaries at the PK Scientist's best knowledge and judgment. All the derived parameters (i.e. <math>t_{1/2}</math>, <math>AUC_{tau}</math>, <math>CL_{ss/F}</math>) will be flagged from statistical analysis accordingly.
 
6. The <math>t_{1/2}</math> will be calculated as follows:
 
 $t_{1/2} = \frac{\ln 2}{\lambda_z} \approx \frac{0.693}{\lambda_z}$ 
Data points may be dropped from the linear regression if the PK Scientist considers the reported values to be anomalous. Any data points so designated should remain in the listings and be identified in the study report with a rationale for exclusion.

$CL_{ss/F}$	Apparent clearance of parent drug will be calculated from: $CL_{ss/F} = Dose/AUC_{tau}$
$R_{trough}$	Ratio between the $C_{trough}$ after the last dose on Day 3 and the pre-dose concentration before each dose with the exclusion of morning dose on Day 1

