2 INTRODUCTION

Product description

Brivaracetam ((2S)-2-[(4R)-2-oxo-4-propyltetrahydro-1*H*-pyrrol-1-yl] butanamide) is a 2-pyrrolidone derivative. The current targeted therapeutic indications for BRV in Japan are monotherapy and adjunctive therapy in the treatment of focal/partial-onset seizures (POS) with or without secondary generalization in patients from 4 years of age with epilepsy.

Brivaracetam displays a high and selective affinity for the synaptic vesicle protein 2A (SV2A) in the brain. Binding to SV2A is believed to be the primary mechanism for BRV anticonvulsant activity (Matagne et al, 2008).

More detailed information regarding the nonclinical and clinical development programs for BRV, including all completed and ongoing studies, can be found in the latest version of the Investigator's Brochure (IB).

Pharmacokinetics

Brivaracetam is rapidly and completely absorbed throughout the gastrointestinal tract. The median t_{max} is 1hr (range: 0.25 to 3hr) after dosing in fasting participants. The pharmacokinetics (PK) of BRV is dose proportional from 10mg to at least 600mg (for single dose). A food-effect study involving administration of BRV to healthy participants under fasting conditions and with a high-fat, high-calorie meal indicated that under fed conditions the C_{max} was decreased by 28% and t_{max} occurred 3hr later, while the AUC remained unchanged. The decrease in absorption rate is not clinically significant; therefore, BRV can be taken without regards to meals.

Brivaracetam follows single-compartment first-order PK, without an apparent distribution phase. The volume of distribution is 0.5L/kg, a value that is close to the volume of total body water. Brivaracetam is weakly bound to plasma proteins (<20%). The plasma half-life of BRV is approximately 9hr in healthy adults. More than 95% of the dose, including less than 9% as unchanged BRV, is excreted in the urine within 72hr after dosing. Fecal and expired air excretion account for <1% of the dose.

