8.6 Pharmacokinetics

Blood samples of approximately 4mL will be collected for measurement of plasma concentrations of BRV as specified in the Schedule of Activities (Section 1.3) Instructions for the collection and handling of biological samples will be provided by the Sponsor. The actual date and time (24hr clock time) of each sample will be recorded.

Samples will be used to evaluate the PK of BRV. Each blood sample will be divided into 2 aliquots (1 for PK and 1 as a backup). Samples collected for analyses of BRV plasma concentration may also be used to evaluate safety aspects related to concerns arising during or after the study.

The primary and other PK endpoints are provided in Section 3. These will be calculated by the contract research organization (CRO). Details of the PK methods used for the calculations of the parameters are outlined in the Statistical Analysis Plan (SAP). Definitions for these PK endpoints are as follows:

- AUC_{tau} area under the curve during a dosing interval at steady state
- $CL_{\text{ss/F}}$ apparent total body clearance at steady state
- $C_{\text{max,ss}}$ maximum plasma concentration at steady state
- C_{trough} measured concentration at the end of a dosing interval at steady state
- $t_{\text{max,ss}}$ time of $C_{\text{max,ss}}$

Brivaracetam concentration will be determined in study plasma samples using a validated liquid chromatography electrospray ionization tandem mass spectrometry bioanalytical method. The lower limit of quantification will be 2ng/mL. The assays will be performed in accordance with International Council for Harmonisation (ICH) guideline M10 on bioanalytical method validation and study sample analysis, January 2023.

Blood sampling time for PK analysis is provided below, and a blood sampling scheme is provided in [Figure 4-1](#).

- Day 1 (before the morning and evening doses [0 and 12hr post the initial dose])
- Day 2 (before the morning and evening doses [24 and 36hr post the initial dose])
- Day 3 (before the morning [only] dose [48hr post the initial dose] and 10min, 15min, 20min, 30min, 45min, 60min, 75min, 90min, 2hr, 6hr, 9hr, and 12hr postdose)

Study sites should aim to collect PK samples at the nominal time points to the extent possible. However, the maximum deviations from scheduled sampling times considered irrelevant for PK are defined in [Table 8-1](#).

Table 8-1: Irrelevant time deviations for PK sampling

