### 3.4 Pharmacokinetic Set

The Pharmacokinetic Set (PKS) consists of all study participants who are randomized, receive at least 1 dose of active IMP and have at least 1 quantifiable post-Baseline PK measurement.

All PKS participants who have a sufficient number of bioanalytical assessments to calculate reliable estimates for the primary PK parameters for both BRV formulations will be included in the statistical analysis.

If a participant's predose concentration on Day 1 is greater than 5% of the  $C_{max,ss}$  value on Day 3 in a Dosing Period, the participant's data from that Dosing Period will be excluded from the statistical analysis. If a participant's predose concentration on Day 1 is greater than 5% of the  $C_{max,ss}$  value on Day 3 for both Dosing Periods, the participant will be excluded from the statistical analysis.

If vomiting occurs at or before 2 times the median  $t_{max,ss}$  for the tablet and the dry syrup within a Dosing Period, the participant's data from that period will be excluded from the statistical analysis. If vomiting occurs at or before 2 times the median  $t_{max,ss}$  within a Dosing Period, for both Dosing Periods, the participant will be excluded from the statistical analysis.

If (1) a PK sample is missing and the  $C_{max,ss}$  is the sample immediately preceding or following the missing sample or (2) 2 or more samples are missing, then the participant's data from that period will be excluded from the statistical analysis.

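### SAP Table 6-1 sets a lambda-z window that a 12 h profile with a 9 h half-life cannot meet, and attaches the consequence to the co-primary AUCtau, which normally does not use lambda z

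*SAP*

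**What the plan says.** SAP Appendix 13, Table 6-1, row for lambda z and t1/2, item 5: the interval used to estimate lambda z "should be equal or greater than 1.5-fold the estimated" t1/2. Otherwise the result is flagged, and its use in descriptive summaries is left to the PK Scientist's judgment. The parameters listed as derived (t1/2, AUCtau, CLss/F) "will be flagged from statistical analysis accordingly". Item 4 of the same row leaves Cmax out of the regression and asks for at least three points.

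Other places that bear on this:

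- Protocol Section 2, Pharmacokinetics: "The plasma half-life of BRV is approximately 9hr in healthy adults". Median tmax when fasting is 1 h, range 0.25 to 3 h.
- Protocol Section 8.6: the Day 3 schedule ends "90min, 2hr, 6hr, 9hr, and 12hr postdose". Table 8-1 accepts the 12 h sample from 0 to 5 min late, not early.
- SAP Table 6-1, AUCtau row: the area is a linear up/log down trapezoid. Only when the last usable sample falls before tau is it the case that AUCtau "will be calculated by extrapolation to time" tau with lambda z. AUCtau values are then flagged "based on the reliability of extrapolation".
- SAP Table 6-1, %AUCex row: above 10%, AUCtau and CLss/F "should be flagged and footnoted in parameter listing".
- SAP Section 3.4: for predose carry-over, vomiting or missing samples, the participant's "data from that period will be excluded from the statistical analysis". No lambda-z criterion appears there.

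**The concern.** The window rule is hard to satisfy when the half-life is close to the length of the dosing interval, and here the sampling covers one 12 h interval only. A rule that most profiles miss needs a clear and harmless consequence, and item 5 gives neither.

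Of the three parameters it names, AUCtau is the only one in the mixed model of SAP Section 4.2.2, where it is co-primary with Cmax,ss. Item 4 says only that values are flagged. Item 5 adds the reference to statistical analysis and sets it against descriptive use, so removal from the bioequivalence model is a natural reading. It is not the only one, because the term flag is not defined and the %AUCex row treats it as a listing footnote.

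If the flag removes values, profiles leave a co-primary analysis for a reason unrelated to how well AUCtau was measured, the profiles kept are those with short half-lives, and judgment enters in an open-label study with no sensitivity analysis planned (SAP Section 4.2.3). If it does not, the bioequivalence result is unchanged, but most AUCtau and CLss/F values are marked as doubtful for no good reason, and their place in the descriptive summaries becomes discretionary. (t1/2 is not among the summarized parameters in SAP Section 4.6.1.1.2.)

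**Working it through.** The plan states no figure for how many profiles meet the rule, so there is nothing to reproduce first.

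**1. Window required.** 1.5 × 9 h = 13.5 h, which is longer than the whole 12 h interval.

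**2. Window available.** Because Cmax is left out, window = 12 h − time of the first nominal sample after Cmax. Largest half-life that passes = window / 1.5.

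| Cmax at | First point in fit | Window | Largest passing t1/2 |
|---|---|---|---|
| 10 min | 15 min | 11.75 h | 7.83 h |
| 15 min | 20 min | 11.67 h | 7.78 h |
| 1 h | 1.25 h | 10.75 h | 7.17 h |
| 1.5 h | 2 h | 10.0 h | 6.67 h |
| 2 h | 6 h | 6.0 h | 4.0 h |

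A profile with an estimated half-life of 9 h misses the rule in every row. This step needs no assumption beyond the documents' own figures. A 12 h sample taken the allowed 5 min late adds only 0.08 h to the window.

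**3. Share of profiles that miss it.** The documents give no spread for the half-life, so one is assumed: lognormal, σ = √ln(1 + CV²), CV 10% to 25%. Share missing = 1 − Φ[ln(limit / median) / σ].

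Example with median 9 h, CV 10% and limit 7.17 h: σ = 0.0998, ln(7.167/9) = −0.228, ratio −2.28, share 98.9%.

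| Median t1/2 | Window | CV 10% | CV 25% |
|---|---|---|---|
| 9 h | 10.75 h | 98.9% | 82.3% |
| 9 h | 11.67 h | 92.8% | 72.3% |
| 8 h | 10.75 h | 86.5% | 67.2% |
| 8 h | 11.67 h | 61.1% | 54.6% |

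Under this distribution the share drops to half when the median half-life equals the limit in step 2: about 7.2 h for tmax at 1 h, about 7.8 h for the earliest tmax.

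**4. What removal would leave (median 9 h, CV 10% and 25%).** Of 60 profiles per formulation, 0.7 to 10.6 remain with the 10.75 h window and 4.3 to 16.6 with the 11.67 h window. Their median half-life would be 6.99 and 6.46 h in the first case, 7.52 and 6.89 h in the second.

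**5. Does AUCtau depend on lambda z?** A 12 h sample inside the accepted range has an actual time at or after tau, so no extrapolation occurs. For departures, take one-compartment decay with t1/2 = 9 h, k = ln 2 / 9, and share of AUCtau after time a = (e^(−ka) − e^(−12k)) / (1 − e^(−12k)):

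- Sample 5 min early (a = 11.917 h): 0.42%.
- 12 h sample missing (a = 9 h): (0.5 − 0.397) / (1 − 0.397) = 17.1%, which the existing 10% rule on %AUCex already catches.

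**6. Precision.** With 10 participants complete in both periods, GMR 0.989, CV 2.7% and the interim one-sided level 0.03817: t(0.96183, 8 df) = 2.034, half-width = 2.034 × 0.027 × √(2/10) = 0.0246, CI = 0.989 × exp(±0.0246) = 0.965 to 1.014. In simulation, at GMR 0.9893, AUCtau power is above 99.9% even with 4 complete pairs.

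**The case against.** The best defence has four parts.

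*It is a recommendation with a stated fallback.* Item 5 says should, and provides for profiles that fall short. That is correct, and this note does not treat a short window as a breach. But the fallback is exactly where the unclear consequence for AUCtau sits.

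*The table can be read harmoniously.* Item 5 stands in the lambda-z row and speaks of derived parameters, while the AUCtau row ties its flag to extrapolation. Together they could mean that only an AUCtau actually extrapolated with lambda z is affected, which should be rare. This may be the intent. However, item 5 lists AUCtau by name and without that condition, so the text does not say it.

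*No operative section orders removal.* Neither SAP Section 3.4 nor Section 4.2.2 contains a lambda-z exclusion, and SAP Section 4.1 uses statistical analysis in a wider sense than the mixed model. This stands as far as it goes: removal is one reading and not a settled plan. Against it, Section 3.4 uses the same term for the bioequivalence analysis and also requires reliable estimates of the primary parameters, so an item 5 flag could be cited as evidence that an AUCtau is unreliable.

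*The conclusion would not change.* AUCtau has precision to spare, Cmax,ss drives the power, and in a crossover selection on half-life does not automatically bias the Test/Reference ratio. All of this stands. No reversal of the result and no direction of bias is claimed here. The objection to the rule is that it leaves the content of a co-primary analysis undetermined.

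**Conclusion.** The concern holds. At the protocol's own half-life the rule asks for 13.5 h where the design can give 10.75 to 11.75 h for a tmax of 1 h or earlier, so a profile with a half-life near 9 h always misses it. That most profiles will miss it rests on an assumed half-life distribution, and it remains true across medians of 8 to 9 h with CV 10-25%: from 55% (median 8 h, 11.67 h window) to 99% (median 9 h, 10.75 h window). The 9 h figure is an approximate value for healthy adults, not specific to this population.

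The consequence is attached to a co-primary endpoint that, with an on-time 12 h sample, owes nothing to lambda z. Whether it means removal or a footnote is left open. The matter is one of pre-specification and internal consistency, not of power, and it should be corrected.

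**What to change.** In SAP Table 6-1:

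1. Item 5: apply the window flag to lambda z and t1/2 only, and delete the words from statistical analysis.
2. Flag AUCtau and CLss/F only when lambda z was actually used to extrapolate to tau, through the existing 10% rule on %AUCex.
3. Make the same change to the parameter list in item 4. This is for consistency only; no problem with the R² rule is claimed.
4. Add a sentence such as: *AUCtau values obtained without lambda-z extrapolation are not removed from the mixed model on lambda-z grounds; the exclusions in SAP Section 3.4 (predose above 5%, vomiting, missing samples) still apply.*

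The cost is two table items and one sentence in the SAP, with no new data.
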